8. STUDY COMPLETION

8.1. Early Study Termination

If the Sponsor elects to terminate the study prematurely, the Sponsor will provide appropriate notification to the Investigators, Institutional Review Boards (IRBs), and FDA and other relevant regulatory authorities as applicable. The notification will include instructions for handling patients still on study drug, data collection procedures, and requirements for study close-down.

8.2. Patient Discontinuation

Prior to discontinuing a patient, every effort should be made to contact the patient, schedule a final study visit, obtain as much follow-up data as possible, and retrieve all study material. An attempt will be made to collect survival data whenever possible, unless the patient has withdrawn consent for all study-related activities.

8.3. Lost to Follow-Up

Patients who do not return for scheduled visits and who cannot be contacted, will be considered lost to follow-up. Follow-up attempts will be documented in the source documents and the applicable sections of the eCRF.

9. ASSESSMENT OF SAFETY

9.1. Specification of Safety Parameters

9.1.1. Adverse Event (AE) Definition

An AE is any untoward medical event that occurs to a patient following the start of investigational product (IP) administration, whether the event is considered IP-related or not.

Pre-existing conditions are not considered an AE unless the condition worsens by at least 1 grade following the start of IP administration.

Adverse events will be captured with the first dose of study drugs (on Cycle 1 Day 1) and continue until 28 days after the last dose of study drugs or until a new anticancer treatment is started.

Death considered related to disease progression will not be considered an AE. However, all deaths within 28 days of last study drug administration or assessed as related to study drug, must be reported on a serious adverse event (SAE) form within 24 hours.

9.1.2. Abnormal Laboratory Tests

Laboratory test abnormalities that constitute an adverse event (i.e., are considered to be clinically significant, induce clinical signs or symptoms, require concomitant therapy or require changes in study treatment) should be recorded in the eCRF. If possible, a diagnosis rather than a symptom should be provided (e.g., anemia instead of low hemoglobin). Laboratory abnormalities that meet the criteria for AEs should be followed until they return to normal or an explanation for the abnormality is determined. When abnormal results are due to toxicity, patients should be assessed twice weekly for resolution.

Laboratory abnormalities that do not meet the definition of an AE should not be reported as adverse events. If a dose hold or concomitant medication for the lab abnormality is required, this would be considered an AE by definition and must be reported as such.

9.1.3. Definition of Serious Adverse Events (SAE)

An SAE is any AE that results in any of the following outcomes:

- Death
- A life-threatening experience
- An inpatient hospitalization or prolongation of an existing hospitalization
- A persistent or significant disability/incapacity
- A congenital anomaly/birth defect
- An event that is not listed above but that requires intervention to prevent one of the outcomes listed above also is considered a SAE

Elective hospitalizations for a pre-existing condition that is unrelated to the indication under study and has not worsened since signing the informed consent should not be reported as a SAE.

Hospitalizations related to disease progression should not be reported as a SAE.

9.2. Classification of an Adverse Event

9.2.1. Severity of Event

All AEs will be assessed by the Investigator using NCI CTCAE version 5.0.

9.2.2. Relationship to Study Drugs

The Investigator will use his/her best medical judgment to determine the relationship of an AE to one or both study drugs.

The relationship of an AE or SAE to study drugs will be classified using the following 3 categories:

- Definitely related
- Possibly related

- Unrelated

To be classified as “Definitely related”, an AE should occur in a timeframe relative to administration of study drugs that suggests a strong causal relationship between study drugs and the AE. In addition, there should be no other reasonable explanations for the AE, such as underlying disease or other concurrent conditions.

To be classified as “Unrelated”, an AE should occur in a timeframe relative to administration of study drugs that suggests a causal relationship between study drugs and the AE is very unlikely. In addition, there should be a reasonable explanation for the AE, such as underlying disease or other concurrent condition.

To be classified as “Possibly related”, an AE should not fall clearly into 1 of the above 2 categories. This would include, for example, an AE that does not seem to occur in close temporal proximity to administration of study drugs, but also has no other reasonable explanation.

9.2.3. Expectedness

The Investigator will make an assessment of whether an AE is expected or unexpected. An AE will be considered unexpected if the nature, severity, or frequency of the event is not consistent with the reference safety information described in the Investigator Brochure for the study drugs.

Expectedness refers to AEs previously observed, not to what might be anticipated from the properties of the study agent or what has been seen with agents of the same class.

9.3. Time Period for AE Reporting

Adverse Events will be recorded that occur following the first administration of study drugs (on Cycle 1 Day 1) up to and including 28 days after the last dose of study drugs or until the start of a new anticancer therapy.

10. ASSESSMENT OF EFFICACY

Response will be assessed locally using a combination of physical exam and imaging (e.g., PET-CT scan, CT scan MRI, bone marrow/aspirate) as appropriate for each patient.

Response assessments will follow the Recommendations for Initial Evaluation, Staging, and Response Assessment of Hodgkin and Non-Hodgkin Lymphoma: The Lugano Classification.²²

Response assessments may also be conducted centrally using the RECIL criteria.²³

11. REPORTING PROCEDURES

11.1. Serious Adverse Event Reporting

All SAEs must be reported to the Sponsor within 24 hours of the Investigator becoming aware of the SAE. The time period for reporting SAEs will follow that for AEs as outlined in [Section 9.3](#).

To report a SAE, sites will complete an SAE Report Form and email the report to:

[contact]

or

Fax to [name]

The Investigator should discuss with the Medical Monitor any SAEs for which the issue of seriousness is unclear or questioned. Contact information for the Medical Monitor is:

Name: [name]
[contact]
Email: [contact]

SAEs must be reported by each site to their appropriate IRB/Ethics Committee (EC) in accordance with the timeframes and procedures required by their IRB Policy.

The Sponsor will report SAEs to the US FDA and any other relevant regulatory authorities.

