4.2. Exclusion Criteria

1. Fewer than 14 days from prior anti-lymphoma therapy (chemotherapy, irradiation, biological, or investigational therapy), or fewer than 7 days from prior therapies if approved by the Medical Monitor. Corticosteroid treatment at doses of ≤ 20 mg/day of prednisone or its equivalent, granulocyte colony-stimulating factor (G-CSF) or granulocyte-macrophage colony-stimulating factor (GM-CSF) are permitted up to 2 weeks prior to start of study treatment.
2. Fewer than 28 days from receipt of prior HDAC inhibitor
3. Fewer than 60 days from prior hematopoietic stem cell transplantation or solid organ transplantation
4. Known primary CNS lymphoma
5. CNS metastases or leptomeningeal disease unless appropriately treated and neurologically stable for at least 4 weeks
6. Other known active cancer(s) likely to require treatment in the next year that would impact the assessment of any study endpoints
7. Refractory graft versus host disease (GvHD) not responding to treatment (e.g., steroid refractory and not responding to second-line agents)
8. Active, uncontrolled bacterial, viral, or fungal infection(s) requiring systemic therapy
9. Pregnant or currently breastfeeding
10. Positive hepatitis B core antibody or surface antigen unless quantitative DNA PCR is negative and patient will be receiving prophylaxis for reactivation
11. Positive hepatitis C viral RNA (if serology is positive for infection)
12. History of allergic reactions attributed to compounds of similar chemical or biologic composition to valganciclovir

[figure not shown]
13. Psychiatric illness/social situations that would interfere with compliance with study requirements
14. Clinically significant cardiovascular abnormalities such as uncontrolled hypertension, congestive heart failure (New York Heart Association classification \geq II), unstable angina, poorly controlled arrhythmias, or myocardial infarction within 6 months of study entry. Congenital long QT syndrome or corrected QT interval using Fridericia's method (QTcF) interval of \geq 470 msec, average of triplicate readings at screening.
15. Other severe acute or chronic medical or psychiatric conditions or laboratory abnormalities that would impart, in the judgement of the Investigator, Medical Monitor, and/or Sponsor representative, excess risk associated with study participation or would interfere with study outcome assessments

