3.4.1.1 Primary Safety Endpoints

An AE is any untoward medical event that occurs in a patient following the start of investigational product (IP) administration, whether the event is considered IP-related or not. Pre-existing conditions are not considered an AE unless the condition worsens by at least 1 grade following the start of IP administration. Adverse events will be captured with the first dose of study drugs (on Cycle 1 Day 1) and continue until 28 days after the last dose of study drugs or until a new anticancer treatment is started whichever is first.

Dose-limiting toxicity AEs must meet all of the following criteria:

- Occurs during the first cycle (28 days) of study drug administration in Phase 1b only
- Is not incontrovertibly related to underlying disease
- In addition, to be considered a DLT, the AE will meet at least one of the criteria listed below:
 - Grade 4 anemia unexplained by underlying disease
 - Grade 4 febrile neutropenia
 - Grade 4 neutropenia lasting >5 days
 - Any other Grade 4 hematologic toxicity (thrombocytopenia, neutropenia, febrile neutropenia, anemia) of any duration
 - Grade 4 or higher tumor lysis syndrome
 - Grade 3 or higher thrombocytopenia (with or without bleeding)
 - Any requirement for platelet transfusion
 - Grade 3 or higher non-hematologic toxicity despite adequate supportive care
 - Results in a dose hold of >7 consecutive days

AEs that persist <72 hours and are able to be managed with supportive care may be excluded.

3.4.1.2 *Secondary Safety Endpoints*

Laboratory Parameters

Clinical laboratory evaluations will follow those outlined in the clinical study protocol and will be performed using a central or local laboratory. Evaluations include hematology, chemistry, urinalysis, coagulation, and pregnancy tests (for women of childbearing-potential only). Specific parameters to be collected are listed below:

- Hematology (blood): Complete blood count with differential to include white blood cells and differential, red blood cells, hemoglobin, hematocrit, platelets, mean corpuscular hemoglobin, mean corpuscular volume
- Chemistry (blood): Sodium, potassium, chloride, bicarbonate, blood urea nitrogen, creatinine, glucose, calcium, phosphate, magnesium, aspartate aminotransferase (AST), aminotransferase, alanine aminotransferase (ALT), total bilirubin, alkaline phosphatase, total protein, albumin, uric acid, and lactate dehydrogenase

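### Non-fatal SAEs judged related to study drug have no reporting requirement once new anticancer therapy starts or 28 days have passed since the last dose, and Protocol 11.1 does not point to the separate rule for deaths in 9.1.1

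*Protocol*

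**What the plan says.** Four places set the rule.

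- **Protocol 11.1** has no SAE window of its own: "The time period for reporting SAEs will follow that for AEs as outlined in" Section 9.3. It also sets the speed of reporting: "All SAEs must be reported to the Sponsor within 24 hours of the Investigator becoming aware of the SAE".
- **Protocol 9.3** runs the AE window from the first dose "up to and including 28 days after the last dose of study drugs or until the start of a new anticancer therapy". Section 9.1.1 gives the same two end points: "continue until 28 days after the last dose of study drugs or until a new anticancer treatment is started". Neither says which applies when they differ.
- **SAP 3.4.1.1** repeats the window and settles that question: "or until a new anticancer treatment is started whichever is first".
- **Protocol 9.1.1** adds a rule for deaths: "all deaths within 28 days of last study drug administration or assessed as related to study drug, must be reported" on an SAE form within 24 hours. New therapy does not end this duty, and related deaths have no time limit.

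Later contact under Protocol 6.3.3 covers additional therapy, response status and survival. Adverse events are not on that list.

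**The concern.** Safety and tolerability are a primary objective, and the Safety Review Committee works from what sites report. Under the stated window, whether a related serious event must be reported depends on when the patient starts another treatment, and not only on the event. Patients whose disease progresses and who switch early are observed for less time than those who do not.

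The protocol accepts for deaths that a judgement of relatedness should outlast the window. It gives no reason for treating a life-threatening or disabling related event differently. Its own relatedness scale (9.2.2) allows an event remote in time from dosing to be classed as possibly related when nothing else explains it. The plan thus foresees related events that are distant from dosing but does not require a report of a serious one outside the window.

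The period after the last dose is not an idle worry here. Protocol 1.12.1 expects that overlapping toxicities of the two drugs may increase in combination. Protocol 1.5 reports that three complete responders in the earlier study of arginine butyrate with ganciclovir died shortly after finishing therapy, from comorbid conditions and complications of tumor lysis.

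**Working it through.** No sample-size or event figure underlies this point, so the check sets the rules side by side.

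**Step 1. Which end point governs?** The protocol has a bare *or*; the SAP takes the earlier. Two things in the protocol favour the SAP's reading. Section 3.11 stops documenting concomitant medications at new anticancer therapy if that comes sooner than 28 days. And if the later end point governed, the window would never close for a patient who starts no new therapy. The earlier-of reading is used below.

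**Step 2. Apply each rule.** Days count from the last dose.

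| Event | 9.3 with 11.1 | 9.1.1 death rule | Report required? |
|---|---|---|---|
| SAE starting before any switch and by Day 28 | Inside | Not needed | Yes |
| Non-fatal related SAE after a switch, by Day 28 | Outside | Does not apply | **No** |
| Non-fatal related SAE after Day 28, switched or not | Outside | Does not apply | **No** |
| Any death after a switch, by Day 28 | Outside | Applies | Yes, but only through 9.1.1 |
| Related death after Day 28 | Outside | Applies | Yes, but only through 9.1.1 |

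For example, suppose a patient switches on Day 10 and has a related serious event on Day 20. If the event is fatal, 9.1.1 requires an SAE form. If the patient survives, nothing does. A site that reads only the reporting section would not learn of the duty in the fatal case either.

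**Step 3. Does another provision close the gap?**

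- The 24-hour rule in 11.1 sets speed. It does not lengthen the window.
- Table 15 includes adverse events at the Safety Follow-Up Visit, 28 ± 7 days after the last dose, so as late as Day 35 (28 + 7). It states no waiver for switched patients, but does not say that it extends the 9.3 window.
- Protocol 9.1.2 follows laboratory abnormalities that meet the AE criteria until they return to normal or are explained. That covers the course of such an event, not new onsets outside the window.
- The treatment-emergent definition in SAP 4.5.2 has no end date, so it would not exclude a late event. The event must still be collected to reach a table.
- SAP 4.5.3 lists all deaths, including those in post-treatment follow-up, but that does not help with non-fatal events.

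**Step 4. Size.** The documents give neither the share of patients who switch within 28 days nor the timing of switches. No count of affected patients or events follows from them.

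**The case against.** **There is no contradiction on deaths.** Section 9.1.1 states the window and then adds the death rule as a special duty, much as 11.3 requires an SAE form for an overdose even without an adverse event. Nothing in 9.3 or 11.1 forbids the extra report, so a site can comply with both. This stands. A reader might infer that 11.1 and 9.1.1 conflict outright, but the better reading is a general rule and a specific rule with a missing cross-reference.

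**Related events are not ignored altogether.** A reader might infer that the protocol makes no exception at all for drug-related events. It does, for related deaths. The gap is confined to non-fatal events that start outside the window.

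**Nothing shows that events will be missed.** A reader might infer that delayed cytopenia or renal toxicity will go unrecorded. The documents do not show that. No passage describes toxicity that first appears after stopping; the median half-life of VRx-3996 was 1.8 hours with no apparent accumulation (1.8). The follow-up visit includes hematology and chemistry. Section 16.1 also binds investigators to outside regulations whose content cannot be examined here. What is shown is a missing protocol requirement.

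**The loss cannot be sized from the entry washouts.** Exclusion 1 ("Fewer than 14 days from prior anti-lymphoma therapy", or fewer than 7 with Medical Monitor approval) might tempt a reader to assume switches on Day 14 or Day 7, and so a loss of (28 − 14)/28 = 50% or (28 − 7)/28 = 75% of the window. Those are shares of calendar days, not of events or patients, and an entry washout says nothing about when patients leaving this trial start other treatment.

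**Closing at new therapy is a legitimate choice.** It avoids attributing another drug's toxicity to this one, in a descriptive study with no formal comparison of cohorts. The Phase 2 boundaries count DLTs, and the DLT definition is limited to the first cycle of Phase 1b, so late SAEs would seldom affect them. This is a good reason to keep the window for AEs and unrelated SAEs. It is weaker for serious events that the investigator has already judged related.

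**Conclusion.** The point holds in a limited form. Read with the SAP, Protocol 9.3 and 11.1 leave a non-fatal related SAE without a reporting requirement if it starts after new anticancer therapy or more than 28 days after the last dose. The second route does not depend on switching. Separately, 11.1 omits the 9.1.1 death rule, and the protocol and SAP do not state the window in the same terms.

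The gap after a switch and before Day 28 rests on the earlier-of reading, which the SAP states and Section 3.11 supports but Sections 9.1.1 and 9.3 leave open. The size is unknown and probably small in number of events. It is still worth correcting, because safety is a primary objective and the correction costs little.

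**What to change.** 1. Keep the current window for AEs and for SAEs assessed as unrelated.
2. In Protocol 9.3 and 11.1, state that any SAE assessed as definitely or possibly related to study drug is reportable whenever it occurs, including after new anticancer therapy has started.
3. In 11.1, cross-refer to the death rule in 9.1.1.
4. In 9.1.1 and 9.3, say that the window ends at the earlier of the two end points, as the SAP does.
5. Carry the sentence on related SAEs into SAP 3.4.1.1, and flag in tables and listings those that start after new therapy, so that results can be read with and without them.

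The cost is protocol and SAP wording and a few extra SAE forms, with no added visits. The main downside is that attribution after new therapy is confounded, and the possibly-related category in 9.2.2 is broad enough to admit such events. The flag deals with this in the analysis. For patients already past the window, an amendment may not recover events that were never collected, so the study report should state the window that applied to them.

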11.2. Reporting of Pregnancy

Pregnancies occurring in study patients will be reported to the Sponsor within 24 hours of becoming known to the site. A Pregnancy Report Form provided by the Sponsor will be completed. Pregnancies may also be reported to the IRB as per the IRB's requirements.

All pregnancies will be followed to term. Every effort will be made to obtain the health status of the mother and infant or the fetus (in cases of miscarriage or therapeutic abortion).

11.3. Overdose

An overdose is defined as the intake of a study drug in excess of the prescribed daily dose. Since both study drugs are in solid form, this would involve taking an additional 5 mg capsule of VRx-3996 or an additional 450 mg tablet of valganciclovir over the intended dose.

All overdoses, whether accidental or intentional, should be reported on an SAE form whether or not an AE occurred. If an overdose resulted in an AE, the SAE form should specify the event and explain in the narrative that the event was associated with an overdose.

12. STATISTICAL CONSIDERATIONS

12.1. Analysis Datasets

This study will identify the following datasets:

- Intent to treat dataset: All patients who have enrolled in the study
- Safety dataset: All patients who receive at least 1 dose of VRx-3996.
- Efficacy dataset: All patients with measurable disease at Screening who have met all inclusion criteria and have received at least 1 post-baseline tumor assessment for efficacy.

12.2. Description of Statistical Methods

Analyses performed for this study will utilize descriptive statistics. For continuous variables, the following information will be presented by cohort and study phase: n, mean, standard deviation, median, minimum, and maximum. Baseline will be the last observation prior to treatment. For categorical variables counts and percentages will be used.

The clinical outcomes of primary interest are overall response rate (ORR: complete or partial response) and duration of response (DoR). Efficacy will be presented as the percentage of patients with CRs, PRs, and SD. ORR will be calculated as CR + PR; disease control rate will be calculated as CR + PR + SD. Response criteria will follow the recommendations of Cheson et al., 2014.²⁸ The analysis of study data will be based on patient data from both the dose escalation (Phase 1b) and dose expansion (Phase 2 and Tablet cohort) parts up to the time when: i) all Phase 1b patients have completed at least 12 months of follow-up from their first disease response assessment after 2 cycles of therapy or have discontinued from the study, and ii) all patients have been followed for DoR for a maximum period of 12 months from the first dose of study medication, have died, withdrawn consent, discontinued, or are lost to follow up, whichever occurs first. The additional data for any patients continuing to receive study drugs or remaining in safety or survival follow-up beyond the final cutoff point will be summarized in a final Clinical Study Report.

The ORR and CR rates will be summarized by cohort and study phase with exact 95% confidence Intervals (CIs).

Duration of response is defined as time from date of first observed complete or partial response to the date of disease progression, death due to any cause, or last adequate (radiographic) response assessment. The DoR will be estimated for the RP2D dose patients using Kaplan-Meier estimates where patients still on treatment after 12 months will be censored.

